NCT#: NCT04138017

Document Date: 19 August 2021

PROTOCOL

Background

1. Provide the scientific background, rationale and relevance of this project.

INSTRUCTIONS

- This should include a referenced systematic evidenced-based review when possible.
- If this study involves qualitative research explain the major constructs of your study.
- Do not state in this section what you plan to do in this study. This information should be entered later under "What will be done in this protocol?"
- Do not include the bibliography in this section.
- For studies submitted under the Expedited review criteria, this section need not be more than a few paragraphs.
- For those studies where data will be analyzed collaboratively by multiple sites doing
 a similar study for which there is no common protocol (Collaborative Site Analysis
 Study) include a description of the common scientific goals/ procedures/data points.
- If this is a FIVE YEAR UPDATE make sure the information throughout the protocol includes the most current information.

Answer/Response: Arthrodesis procedures for the ankle and hindfoot are performed to correct deformity and treat end-stage arthritis. However, recent literature has demonstrated that 10-40% of ankle fusions result in non-union (1,2). For triple arthrodesis (talonavicular, subtalar, and calcaneocuboid joints), published rates of non-union range from 0-10% (3). However, recent literature from our institution demonstrated significantly higher rates of non-union when calcaneo-cuboid sparing hindfoot arthrodesis was performed (4). Given that not every non-union results in a revision surgery, it is likely that the published rates of non-union underestimate the true rate of this complication. Due to the extended period of convalescence after these major arthrodesis procedures, non-union is a devastating outcome. Loss of mobility, loss of income from employment, and increased health care expense and patient risk for a second procedure contribute to the economic and emotional impact of non-union upon these patients.

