If this study involves biomedical research clearly state the objectives and hypotheses and clearly define the primary and any secondary outcome measures. If this study involves qualitative research clearly state your research hypothesis or question.

This section should not include information already included in other sections such as background information or information from the procedures section.

Answer/Response: To evaluate 1-Year implant survivorship in subjects who receive the implant when used for primary ankle or hindfoot arthrodesis procedures.

Study Design: Biomedical

1. Will controls be used?

Answer/Response: No.

► IF YES, explain the kind of controls to be used.

Answer/Response:

2. What is the study design?

Example: case series, case control study, cohort study, randomized control study, single-blind, double-blind, met-analysis, systematic reviews, other. You may also view the IRB-HSR Learning Shot on this topic to help you answer this question. (http://www.virginia.edu/vpr/irb/learningshots/Writing protocol June09/player.html

Answer/Response: This is a post-market, prospective, non-randomized, PI initiated, open-label clinical evaluation of the implant for use in primary ankle or hindfoot

Version Date: 08/19/2021 Page Number: 2 of 10

arthrodesis. Data will be collected at specific time points and entered into case report forms (CRFs) based on the information contained in the patient medical records.

3. Does the study involve a placebo?

Answer/Response: No.

▶ IF YES, provide a justification for the use of a placebo

Answer/Response:

Human Participants

 Ages:
 18-80

 Sex:
 All

 Race:
 All

Subjects- see below

INSTRUCTIONS: For question 1-4 below insert an exact #. Ranges or OPEN is not allowed. This # should be the maximum # you expect to need to enroll (i.e. sign consent) If you are only collecting specimens the number of participants should equate to the # of specimens you need. If you are collecting only data from a chart review the number should designate the number of subjects whose medical records you plan to review. Age/ Sex/Race criteria should designate the demographics of participants from whom you will obtain the specimen/data.

1. Provide target # of subjects (at all sites) needed to complete protocol.

INSTRUCTIONS: If this is NOT a database protocol, this number should be the same as the number of subjects needed to obtain statistically significant results.

Answer/Response: 15

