- Prior infection at site of planned arthrodesis
- Inability to maintain non-weight bearing status
- Bone defect requiring more than 10 cc of bone graft material
- A Vitamin D level of < 30ng/mL pre-operatively
 - -Testing can be completed up to 1 week prior to surgery
- Inadequate bone stock to allow for rigid internal fixation.
- BMI greater than 40
- Pregnancy per review of current lab results in medical record of childbearing females.
- Cognitive inability to provide informed consent
- Tobacco or nicotine use 6-weeks prior to surgery
- Hemoglobin A1C >8.0
- Not-English speaking individuals

Version Date: 08/19/2021 Page Number: 4 of 10

3. List any restrictions on use of other drugs or treatments.

Answer/Response: N/A.

Statistical Considerations

1. Is stratification/randomization involved?

Answer/Response: No.

► IF YES, describe the stratification/ randomization scheme.

INSTRUCTIONS:

The stratification factors and/or the randomization plan should be identified. If there is no randomization component or important patient characteristics that will be used in treatment allocation or data analysis, a statement to this effect should be included.

Stratification factors: These are pretreatment patient characteristics which could be balanced across treatment arms by design or may be used to determine starting dose or treatment allocation.

If randomization is going to be used, the details of the randomization plan should be described.

The description should include:

- -- the method and timing of randomization
- --the type of randomization scheme that will be used in the study
- --whether or not the randomization masked/blinded/if so, then to whom is it masked/blinded
- --who has access to the randomization scheme

Answer/Response: NA

▶ IF YES, who will generate the randomization scheme?

Sponsor			
UVa Sta	itistician.	Insert name	Answer/Response
UVa Investigational Drug Service (IDS)			
Other:	Specify	Answer/Respo	onse:

2. What are the statistical considerations for the protocol?

The objectives section and the statistical section should correspond, and any objective for which analysis is unfeasible should be deleted. Also, the estimates and non-statistical assumptions of the statistical section should be supported by discussion in the background section.

The answer to this question should include:

--Study Design/Endpoints

Version Date: 08/19/2021 Page Number: 5 of 10

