- --Recap of study objectives and endpoint definitions. An assessment of how study objectives will be assessed by identifying & defining which endpoints will be used to assess each component of the study objectives.
- --The study design should include contingencies for early stopping, interim analyses, stratification factors (If applicable), and any characteristics to be incorporated in analyses.
- --The power/precision of the study to address the major study endpoint(s), the assumptions involved in the determination of power/precision.
- --If statistical hypothesis testing is included then specify the null and alternative hypotheses, the test statistic, and the type I and II error rates
- --If precision of an estimate, then provide a definition for precision
- --If other, then specify

Answer/Response: We will compare primary outcome measures as a binary outcome using chisquare or Fisher exact analyses using existing failure rates as a historical control. We will use standard parametric statistical analyses to determine change from pre-post surgery and referencing historical control data obtained from the literature. Multivariate statistical modelling will be considered for potential sources of confound if appropriate.

3. Provide a justification for the sample size used in this protocol.

Include the anticipated accrual rate, the accrual goal for the study, including accrual goals by strata if appropriate, adjustments for drop-outs etc. and study duration.

Answer/Response: ViviGen is already an FDA approved biologic, therefore a large sample size is not needed.

4. What is your plan for primary variable analysis?

Include a sketch of the analysis to assess primary study objectives.

Answer/Response: Radiographic evidence of successful arthrodesis confirmed on CT (defined by >50% fusion)

5. What is your plan for secondary variable analysis?

Include the following:

- -- A sketch of the analysis to assess secondary study objectives.
- --For phase III studies, the power/precision of the study to address the secondary objective(s).

Answer/Response:

- Clinical & Radiographic evidence of failure (obvious non-union or hardware failure)
- Patient reported outcomes scores
- Vitamin D levels

6. Have you been working with a statistician in designing this protocol?

Answer/Response: No.

IF YES, what is their name?

Answer/Response:

Version Date: 08/19/2021 Page Number: 6 of 10

7. Will data from multiple sites be combined during analysis?

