VISITS 5, 6, and 7 –3 months, 6 months and 12 months Post-Surgery

The following procedures will be done as **part of your clinical care.** The results will be recorded for research purposes:

- Physical assessment of hindfoot/ankle, including vital signs
- X-rays of the hindfoot/ankle

The following procedures/assessment will be done solely for research purposes:

- Questionnaires
- Blood draw (1 ½ teaspoons) and analysis for Vitamin D levels (only at the 6 month visit)
- CT scan of your ankle/hindfoot
- At the conclusion of Visit #7, participation in the study is complete.
- 2. If this protocol involves study treatment, explain how a subject will be transitioned from study treatment when they have completed their participation in the study.

Example: If the subject will be taking an investigational drug, will they need to be put back on an approved drug when they have completed the study? If yes, explain how this will be accomplished and who will cover the cost. If the subject has a device implanted will it be removed? Again- who will cover the cost of the removal? **Instructions:** Answer NA if this study does not involve a study treatment.

Answer/Response: N/A.

Subject Compliance with Study Procedures

1. **Explain how the study team will monitor the subject for compliance with the study procedures.** (e.g. study team will administer study drug/ study interventions, study drug inventory of dispensed and returned drug, diary etc.)

Answer/Response: Study visits coincide with standard of care follow-up visits to their surgical procedure.

2. **Describe criteria for when a subject is considered to be non-compliant with study procedures.** (e.g. subject returns more than 20% of the study drug, subject misses 20% of study visits)

Answer/Response: Subject misses 30% of study visits

Bibliography

Version Date: 08/19/2021 Page Number: 9 of 10

- 3. K.L. Wapner. Triple arthrodesis in adults. J Am Acad Orthop Surg, 6 (1998), pp. 188–196

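### The primary test sets a cohort selected for low risk against unnamed literature failure rates that need not come from comparable patients, so a significant result could reflect patient selection rather than the graft

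*Combined protocol and SAP*

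**What the plan says.** Study Design, question 2, describes the study: "This is a post-market, prospective, non-randomized, PI initiated, open-label clinical evaluation of the implant". Question 1 of that section says no controls are used. The target is 15 subjects, with 18 enrolled. The primary variable (Statistical Considerations, question 4) is fusion of more than 50% on CT.

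Statistical Considerations, question 2, compares the primary outcome by chi-square or Fisher exact test, "using existing failure rates as a historical control". It names no rate, source, hypothesis, direction or significance level. It adds that multivariate modelling for confounding will be considered if appropriate, without naming covariates.

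The exclusion list includes "Tobacco or nicotine use 6-weeks prior to surgery" and "Hemoglobin A1C >8.0". It also excludes BMI above 40, vitamin D below 30 ng/mL, prior infection at the site, defects needing more than 10 cc of graft, bone stock too poor for rigid fixation, and patients who cannot stay non-weight bearing.

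The Background gives the candidate benchmarks:
- **Ankle:** "recent literature has demonstrated that 10-40% of ankle fusions result in non-union".
- **Triple arthrodesis:** 0-10% non-union.
- **CT-confirmed fusion:** 84% with rhPDGF-BB and 65% with autograft, that is 16% and 35% failure.

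It does not describe who was eligible for any of these studies. Bibliography reference 1, one of two sources for the ankle range, is titled "A review of ankle arthrodesis: predisposing factors to nonunion".

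**The concern.** Comparison with a historical rate is informative only if that rate is what the enrolled patients would have had under the comparator treatment. Here the enrolled patients are chosen to be free of several conditions that the protocol itself treats as reasons not to enrol. If the historical series included such patients, and they failed more often, the cohort would be expected to do better than history with no contribution from the graft. The planned test would report that as a difference from the historical control.

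The plan has no safeguard against this. It does not require a benchmark with similar exclusions. The optional modelling would use only the 15 to 18 treated patients, and no patient-level historical data are planned, so it cannot adjust for a difference between this cohort and a literature rate. What is at stake is the meaning of a significant primary result.

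**Working it through.** **The plan's own figure.** The only sample-size arithmetic is the allowance for losses: 15 / (1 - 0.10) = 16.7, so 17. The stated 18 is consistent with this. The target of 15 cannot be reproduced, because no error rate, power or benchmark is given.

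**Inputs.** From the documents: n = 15, and historical failure rates p0 of 40% (upper end of the ankle range), 35% (100% - 65%), 16% (100% - 84%) and 10% (lower end of the ankle range and upper end of the triple range). Assumed, because the documents do not give them:
- a share f = 30% or 50% of historical patients with an excluded risk factor;
- a relative risk of failure RR = 1.5, 2 or 3 in those patients;
- a two-sided 5% level;
- a graft no better than the comparator treatment behind each rate.

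**Cut-off.** I used an exact binomial test, which treats the historical rate as known. P(1 or fewer failures of 15) is 0.0052 at p0 = 40% and 0.0142 at 35%. P(2 or fewer) is 0.0271 and 0.0617. With 0.025 in the lower tail, the test rejects at 1 or fewer failures in both cases. The actual size is therefore 0.5% and 1.4%.

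**Effect of selection.** If the historical series mixes both kinds of patient, the failure risk in those eligible here is p_e = p0 / ((1 - f) + f × RR). The false-positive rate is P(X ≤ 1) for X ~ Binomial(15, p_e). Example: p0 = 40%, f = 50%, RR = 3 gives p_e = 0.40 / (0.5 + 1.5) = 20% and P(X ≤ 1) = 16.7%.

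| f | RR | p_e (p0 = 40%) | False positive | p_e (p0 = 35%) | False positive |
|---|---|---|---|---|---|
| 30% | 1.5 | 34.8% | 1.5% | 30.4% | 3.3% |
| 30% | 2 | 30.8% | 3.1% | 26.9% | 5.9% |
| 30% | 3 | 25.0% | 8.0% | 21.9% | 12.8% |
| 50% | 1.5 | 32.0% | 2.5% | 28.0% | 5.0% |
| 50% | 2 | 26.7% | 6.2% | 23.3% | 10.3% |
| 50% | 3 | 20.0% | 16.7% | 17.5% | 23.3% |

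**The lower benchmarks.** With no failures in 15, the one-sided p-value is 0.84^15 = 0.073 against 16% and 0.90^15 = 0.206 against 10%. No result can be significant there.

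**Check with the planned test.** Two-sided Fisher exact against assumed historical groups of 50, 100 or 300 rejects 35% at 1/15 and not at 2/15. It also rejects 40% at 1/15. At 2/15 against 40%, p = 0.068, 0.050 and 0.055, so only the group of 100 is on the border. Against 16% or 10%, 0/15 is not significant with any of the three.

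**Exact two-sided 95% upper limits for the failure rate.** 0/15: 21.8%. 1/15: 31.9%. 2/15: 40.5%.

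**The case against.** Several objections have force.

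- **Historical eligibility is not in the documents.** A reader might infer that the published rates come from patients who were not screened in this way. The title of reference 1 points in that direction for one source of one figure, but it does not establish the criteria. The documents support only that the rates are quoted without eligibility and need not match.
- **There is an opposite bias.** The Background says published non-union probably understates the true rate, because not every non-union leads to revision. That reason does not carry over readily to CT-confirmed rates. A reader might therefore conclude that selection acts unopposed against the 84% and 65% figures. The documents do not show that either: the bibliography identifies the source as a randomized trial, and its exclusions and CT threshold are not given. The mix of procedures could also shift the comparison either way.
- **The 35% rate is an autograft result.** The calculation there concerns a graft equal to autograft, and a reader should not take it to describe an inert material.
- **The size depends on the cut-off.** Rejecting 40% at 2/15 under a one-sided 5% rule would give 6-40% over the same assumptions. The plan states no one-sided test, and the two-sided upper limit for 2/15 (40.5%) does not exclude 40%.
- **No superiority hypothesis is stated.** The objective is one-year survivorship. Still, a significance test against historical failure is the planned primary comparison, so a significantly low failure rate invites that reading.

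These limit the size and certainty of the point. They do not supply what is missing, which is any demonstration that the benchmark applies to this cohort. Two unquantified biases do not make the comparison valid.

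**Conclusion.** The point holds in a limited form. The plan tests a deliberately low-risk cohort against rates it neither names nor shows to be comparable, so a significant result could reflect selection rather than the graft. The documents do not establish that it would, nor the net direction of bias.

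Under the stated assumptions, the chance of a false positive rises from 0.5% to about 1.5-17% against 40% failure, and from 1.4% to about 3-23% against 35%. Compared with 2.5% in the favourable tail, all six settings exceed it at 35% and four of six at 40%. Those are the two quoted rates that a cohort of 15 could beat. Against 16% or 10% a false claim cannot arise at this sample size, so it would be wrong to say that the error rate fails whichever benchmark is used. The prevalence, relative risk and significance level are my assumptions and not figures from the plan.

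**What to change.** Replace the primary chi-square or Fisher test with estimation:

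1. Report the 12-month CT failure proportion with its exact two-sided 95% confidence interval, beside the published rates.
2. Report the upper limit as the lowest benchmark the data would beat: 21.8% for 0/15, 31.9% for 1/15, 40.5% for 2/15. Readers can then judge it against whatever rate they think plausible for low-risk patients.
3. State that a rate lower than published cannot be attributed to the graft.
4. Keep a test only if a single CT-confirmed benchmark, from a series with comparable exclusions, is named before any outcome data are seen. A separate benchmark for each procedure is not practical: 15 patients over four procedure types is about four each if evenly split.

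The cost is protocol wording and one line of analysis, with no extra patients or procedures. The downside is a more modest claim.

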Currently, many alternatives to autograft harvest are being evaluated for foot and ankle arthrodesis. Given the known complications of autograft harvest (incision pain, nerve injury, infection, 1), alternatives which possess osteogenic, osteoconductive, and osteoinductive properties are an attractive option when supplementing complex hindfoot arthrodesis procedures. A recent publication demonstrated a superior fusion rate for purified recombinant human platelet-derived growth factor BB homodimer (rhPDGF-BB) when compared to autograft (5). However, arthrodesis rates, as confirmed on CT scan, were only 84% and 65% respectively.

ViviGen (Depuy Synthes) is a cellular bone matrix, which includes viable osteoblasts within a corticocancellous and demineralized bone carrier, represents a unique alternative to autograft or existing products which utilize mesenchymal stem cells. ViviGen Cellular Bone Matrix is a Human Cells, Tissues, and Cellular and Tissue-based Product (HCT/P) as defined by the U.S.

Version Date: 08/19/2021 Page Number: 1 of 10

Food and Drug Administration in 21 CFR 1271.3(d). ViviGen Cellular Bone Matrix is processed from donated human tissue, resulting from the generous gift of an individual or his/her family. This product is classified as a **biologic** by the FDA. Given our encouraging early data using Vivigen for complex and revision arthrodesis procedures in the foot and ankle, our Foot and Ankle Clinical research group at the University of Virginia wishes to conduct a prospective study to evaluate 1-Year implant survivorship in subjects who receive the implant when used for primary ankle or hindfoot arthrodesis procedures as part of their clinical care.

Our study would prospectively follow primary ankle or hindfoot arthrodesis procedures. Ankle arthrodesis, tibiotalocalcaneal arthrodesis, subtalar and triple arthrodesis procedures would be included in this cohort, and CT scan would be utilized to demonstrate successful arthrodesis (defined by >50% fusion). Patient outcome measures including Foot and Ankle Activity Measures, AOFAS hindfoot score, and VAS pain scores would be recorded pre-operatively and for 1 year post operatively.

The purpose of this study is to examine 1-year outcomes. ViviGen Cellular Bone Matrix is being given as part of clinical care. The only research procedures are questionnaires and blood draw for Vitamin D.

Objectives/Hypothesis

INSTRUCTIONS:

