If you decide to be in this study, you will read and sign this consent form before any study related procedures take place. You will meet with the study doctor to determine if you are eligible and it is safe for you to participate in the study. This will include the following:

The following procedures will be done as **part of your clinical care** and recorded for research purposes in preparation for your arthrodesis surgery.

- Reviewing your medical history, including your smoking history and current alcohol use.
- Physical exam as well as your weight and height
- Review your current medications.
- If you are a female and able to have children, your physician will ask if you are pregnant and may perform a urine or serum pregnancy test to confirm that you are not pregnant.
- If you are not already currently taking Vitamin D supplements, it will be prescribed to you by your surgeon as part of your standard of care before surgery

The following procedures/assessment will be done solely for research purposes:

- Complete study questionnaires that will ask you about your level of pain, your daily activities, physical function, and quality of life. The questionnaires will take about 20 minutes to complete.
- Laboratory testing including collection of blood samples (1 ½ teaspoons)
 - o Your blood will be analyzed to assess your Vitamin D levels

VISIT 2: SURGERY (as part of your clinical care) (will last about 2 ½ hours):

The following procedures will be done as **part of your clinical care** in preparation for your arthrodesis surgery. The results will also be recorded for research purposes:

- Recording of admission and surgical information from your medical chart
- Primary ankle or hindfoot arthrodesis using the ViviGen graft
- Surgical images of the hindfoot/ankle (intra-operative fluoroscopy and post-operative x-ray)

FOLLOW-UP (each visit will add about 45 minutes to your visit): VISIT 3 –2 Weeks Post Surgery

The following procedures will be done as **part of your clinical care.** The results will be recorded for research purposes:

- Wound Check
- Physical assessment of the hindfoot/ankle, including vital signs

VISIT 4 - 6 Weeks Post Surgery

Version Date: 08/19/2021 Page Number: 8 of 10

The following procedure will be done as **part of your clinical care.** The results will be recorded for research purposes:

- Physical assessment of the hindfoot/ankle, including vital signs
- X-rays of the hindfoot/ankle

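### Scores are collected at baseline, 3, 6 and 12 months, but the planned pre-post change fixes no post-surgery visit and no handling of missing 12-month scores.

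*Combined protocol and SAP*

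**What the plan says.** - **Scales.** The Background names "Foot and Ankle Activity Measures, AOFAS hindfoot score, and VAS pain scores would be recorded pre-operatively and for 1 year post operatively". The list is introduced as examples, so three is a minimum. Study Procedures, Visit 1, describes the baseline forms more broadly: "Complete study questionnaires that will ask you about your level of pain, your daily activities, physical function, and quality of life".
- **Times.** Visit 1 is the baseline. Questionnaires recur at Visits 5, 6 and 7, headed "3 months, 6 months and 12 months Post-Surgery". Each scale therefore has four planned measurements.
- **Endpoint.** Statistical Considerations, question 5, lists "Patient reported outcomes scores" with no scale, visit or summary measure.
- **Analysis.** Question 2 of the same section says "We will use standard parametric statistical analyses to determine change from pre-post surgery" and refers to historical data from the literature. It states no significance level, repeated-measures method or missing-data rule.
- **Purpose.** The Background says "The purpose of this study is to examine 1-year outcomes". The analysis text does not take this up.
- **Numbers.** Human Participants gives a target of 15, 18 enrolled, and a single 10% rate that covers screening failures as well as later losses. Subject Compliance defines non-compliance as missing 30% of visits and states no consequence for the analysis.

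**The concern.** A pre-post change needs a defined post measurement. Here there are three to choose from on each scale, and nothing prevents the choice from being made after the scores are seen. With no control arm, the pre-post change is the main evidence on patient-reported benefit, so the choice of visit matters.

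The second issue is loss. A simple pre-post test uses two of the four measurements and drops anyone without the second. If a patient doing badly at 6 months is less likely to return at 12, the patients left in the test look better than the enrolled group. The 3- and 6-month scores carry information about those who leave, and a two-point analysis ignores it.

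**Working it through.** **1. The plan's own figure.** 15/(1 - 0.10) = 16.7, so 17; the plan enrols 18, which is close. 10% of 18 is 1.8, about 2 people. Falling from 18 to 15 is 3/18 = 16.7%. Two or three losses are therefore within the plan's numbers, but the 10% includes screening failures, who have no post-surgery scores. Two of 18 lost after 6 months is thus an upper reading of it. Missing 2 of the 7 visits is 28.6%, so a patient can miss both the 6- and 12-month visits and still count as compliant.

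**2. Number of results.** 3 scales x 3 post-surgery visits = 9. Fixing 12 months leaves 3.

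**3. Chance of at least one false positive** (0.05 two-sided per test is assumed):

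- Independent tests: 1 - 0.95^9 = 0.370; 1 - 0.95^3 = 0.143.
- Simulated paired t-tests, n = 15, 40,000 runs, correlation 0 to 0.9 between scales and 0.3 to 0.7 between visits: 0.21 to 0.34 for nine tests, 0.09 to 0.14 for three.
- One scale with a free choice among three visits: about 0.13 instead of 0.05.

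**4. Bias of a paired test when the worst 6-month responders all leave.** Assumptions not in the documents: each score has SD 1, scores are normal, the true 12-month change is 0.8 SD, and k of n = 18 leave, namely those with the lowest baseline-to-6-month change. Then

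bias = k/(n - k) x m x cov(c6, c12)/SD(c6),

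where c6 and c12 are the changes to 6 and 12 months and m is the mean of the k largest expected normal order statistics for n = 18 (1.820, 1.350, 1.066). So m = 1.820 for k = 1, 1.585 for k = 2 and 1.412 for k = 3.

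With equal correlation r between visits, cov/SD = sqrt((1 - r)/2), which is 0.500 at r = 0.5 and 0.387 at r = 0.7.

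| Lost | r = 0.5 | r = 0.7 |
|---|---|---|
| 1 | 1/17 x 1.820 x 0.500 = 0.054 | 1/17 x 1.820 x 0.387 = 0.041 |
| 2 | 2/16 x 1.585 x 0.500 = 0.099 | 2/16 x 1.585 x 0.387 = 0.077 |
| 3 | 3/15 x 1.412 x 0.500 = 0.141 | 3/15 x 1.412 x 0.387 = 0.109 |

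Simulation (4,000 runs) agrees: 0.103 and 0.076 for two lost, 0.149 and 0.114 for three. Against 0.8 SD, the range 0.08 to 0.15 is 10% to 19%.

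With serial correlation r per visit step, cov = 1 - r^2 - r^3 + r and SD(c6) = sqrt(2(1 - r^2)). At r = 0.7, 0.867/1.010 = 0.858, giving 0.170 (two lost) and 0.242 (three). At r = 0.8, 0.648/0.849 = 0.764, giving 0.151 and 0.216.

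**5. Milder loss.** If poor responders are only more likely to leave, the simulated paired bias under equal correlation is about 0.01 to 0.06 SD with two or three lost. For example, if the odds of leaving double per SD of worse 6-month change, two lost gives about 0.03 SD. If loss is random there is no bias.

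**6. A mixed model on all visits.**

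- Equal correlation, loss driven by the 6-month score: within 0.01 SD of the truth.
- Serial correlation, random-intercept model, the same loss: about 0.06 to 0.12 SD of bias remains.
- Loss driven by the 12-month score itself, two lost: about 0.09 to 0.10 SD under equal correlation and 0.14 under serial correlation.
- Random loss: unbiased, with a standard error about 2% to 3% smaller than the paired test's.

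**The case against.** The strongest reply is that the plan is brief rather than wrong. Repeated-measures and mixed models are parametric too, and the stated 1-year purpose already points to 12 months. That is fair as far as it goes: the wording does not commit the study to a paired test on completers. It does not rule one out either, and the purpose statement is not linked to the score analysis.

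Four stronger readings are tempting, and the documents do not support them.

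- *The plan drops patients without a 12-month score.* No missing-data method is named; this is an inference from usual practice.
- *The plan expects 2 of 18 to be lost at 12 months.* The 10% includes screening failures. Patients lost before 3 months also give a mixed model no post-surgery score to use.
- *The false-positive risk is 37%.* That is a ceiling. The tests share the same patients, no significance level is stated, and the figure applies only if nothing changes on any scale at any visit.
- *A mixed model removes the bias.* Step 6 shows it does so only when its covariance is about right and loss depends on recorded scores.

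Size also counts. With two lost, the worst-case bias is about 0.4 of the standard error (0.099 against 1/sqrt(16) = 0.25). With three it is a little over half (0.141 against 1/sqrt(15) = 0.258). If good responders are the ones who leave, the sign reverses.

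**Conclusion.** The point holds as a gap in specification that existing data can largely close. The post-surgery visit is not fixed, so at least nine results are open where the 1-year purpose needs three. At an assumed 0.05, the chance of a false positive is about 21-34% with plausible correlation (37% at most), against about 9-14%.

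The missing-data part is conditional. It applies if a paired completer test is used and poor responders leave after 6 months. The overstatement is then roughly 0.01-0.06 SD for a tendency to leave and up to about 0.08-0.15 SD if the two or three worst all leave, with correlations of 0.5-0.7. Serial correlation makes it larger. The correlations, the 0.8 SD change and the loss mechanisms are all assumptions.

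These are secondary outcomes in a study targeting 15 patients, and the primary CT result does not depend on them. The change is worth making because it is cheap.

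**What to change.** Replace the pre-post sentence for the scores with wording such as:

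> For each scale, a linear mixed model with visit as a four-level factor (baseline, 3, 6 and 12 months) and small-sample degrees of freedom is fitted to all available scores. The baseline-to-12-month change with its 95% CI is the one reported result for that scale; 3- and 6-month results are descriptive. The covariance allows serial correlation, or a random-intercept model is checked against one that does. The number of scores missing at each visit is reported.

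List the scales by name in question 5, so that the number of results is fixed. Make the change before the scores are analysed.

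The cost is protocol wording and a little more analysis work, with no new data or visits. The downside is that the model reduces bias without guaranteeing its removal: some remains if loss depends on the unseen 12-month score or the covariance is wrong. The missing counts per visit let a reader judge how much that could matter.
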